1.2. Summary of Nonclinical Pharmacology

In 2 primary pharmacodynamic (PD) studies, the effect of GB1211 on carbon tetrachloride-induced liver fibrosis in mice was evaluated. The percentage area of Picrosirius Red positive staining in liver sections was significantly reduced in animals given 10 mg/kg GB1211 twice daily (BID; $p = 0.009$), indicating decreased fibrotic collagen deposition in the hepatic parenchyma; and significantly reduced ($p \leq 0.05$) in once daily and BID groups in a second study. The collagen content, measured by hydroxyproline, was also found to be significantly reduced in the BID group of one study. There were no clear significant changes in liver function, liver fibrosis biomarkers, or indicators of the collagen life cycle, with the exception of increased serum ALT with 10 mg/kg GB1211 BID in 1 study. In a secondary PD study, GB1211 showed no cross-reactivity against an industry standard panel of 87 enzyme and radioligand binding assays.

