4.8. Subject Withdrawal and Replacement

A subject is free to withdraw from the study at any time. In addition, a subject will be withdrawn if any of the following criteria are met:

- change in compliance with any inclusion/exclusion criterion that is clinically relevant and affects subject safety as determined by the Investigator (or designee).
- noncompliance with the study restrictions that might affect subject safety or study assessments/objectives, as considered applicable by the Investigator (or designee).
- any clinically relevant sign or symptom that, in the opinion of the Investigator (or designee), warrants subject withdrawal.

In the event of confirmed results for any of the following criteria, dosing of a subject with the IMP will be stopped permanently:

- QTcF increases > 60 msec compared to baseline (predose) and/or absolute QTcF values > 500 msec (confirmed by repeat measurement).
- Systemic exposure for any individual subject is predicted to exceed a C_{max} of 19755 ng/mL and/or an AUC_{0-24} of 52486 ng.h/mL; ie, systemic exposure will be no greater than the lowest exposure at the NOAEL.
- Liver chemistry results:
 1. ALT or AST > 5 x ULN, which is confirmed by repeat
 2. ALT or AST > 3 x ULN, which is confirmed and total bilirubin > 2 x ULN or international normalised ratio >1.5
 3. ALT or AST > 3 x ULN, which is confirmed and the new appearance (ie, onset coincides with the changes in hepatic enzymes) of fatigue, nausea, vomiting, right upper quadrant pain or tenderness, fever, rash,

or eosinophilia (> ULN) felt by the Investigator to be potentially related to hepatic inflammation/injury.

If a subject is withdrawn, the Sponsor will be notified and the date and reason(s) for the withdrawal will be documented in the subject's electronic Case Report Form (eCRF). If a subject is withdrawn, efforts will be made to perform all follow-up assessments, if possible ([Appendix 6](#)). Other procedures may be performed at the Investigator's (or designee's) and/or Sponsor's discretion. If the subject is in-house, these procedures should be performed before the subject is discharged from the clinic. The Investigator (or designee) may also request that the subject return for an additional Follow-up visit. All withdrawn subjects will be followed until resolution of all their AEs or until the unresolved AEs are judged by the Investigator (or designee) to have stabilised.

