7.3.2. Clinical Laboratory Evaluations

Blood and urine samples will be collected for clinical laboratory evaluations (including clinical chemistry, haematology, urinalysis, serology [including coagulation parameters for Part C]) at the times indicated in the Schedule of Assessments in [Appendix 6](#). Clinical laboratory evaluations are listed in [Appendix 2](#). Additional clinical laboratory evaluations will be performed at other times if judged to be clinically appropriate or if the ongoing review of the data suggests a more detailed assessment of clinical laboratory safety evaluations is required.

Subjects will be asked to provide urine samples for drugs of abuse screen and will undergo an alcohol breath test at the times indicated in the Schedule of Assessments in [Appendix 6](#). For all female subjects, a pregnancy test will be performed at the times indicated in the Schedule of Assessments in [Appendix 6](#).

An Investigator (or designee) will perform a clinical assessment of all clinical laboratory data.

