10.1.2 Repeat and Unscheduled Readings

Repeat readings occur when the original vital signs or ECG result requires confirmation. Repeat readings are labelled as 'Repeat' in the listings and replace the original readings in all summaries and changes from baseline presentations and calculations. Prior to dosing, all readings taken in addition to the original reading are defined as predose repeats. Postdose repeat readings are defined as readings collected within 15 minutes of the actual time of the original reading. Where results are taken in triplicate and repeated, the last 3 readings are used in all subsequent calculations.

With the exception of predose results described above, unscheduled readings for vital signs or ECGs are defined as readings collected >15 minutes from the actual time of the original reading. Where results are taken in triplicate, the original reading is defined as the first reading of the triplicate. All results not taken at a scheduled timepoint for other data types (eg, clinical laboratory parameters) are unscheduled. Unscheduled readings are labelled as 'Unscheduled' in the listings. Because unscheduled readings are not associated with any scheduled timepoint, they are excluded from all summaries (with the exception that they may be used as baseline, as stated in [Section 10.1.1](#)).

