10.6.4 Electrocardiogram

The ECG data will be obtained directly from the 12-lead ECG traces. These data include the QT interval calculated using the Bazett correction (QTcB), the QT interval calculated using the Fridericia correction (QTcF), the PR and QT intervals, the QRS duration, and heart rate.

Where ECGs are measured in triplicate (at approximately 2-minute intervals), the mean value will be used in all subsequent calculations. Changes from baseline will be calculated.

Values for ECG parameters outside the clinical reference ranges will be flagged on the individual subject data listings.

The ECG data will be summarised by treatment, together with changes from baseline. Figures of mean ECG data and mean change from baseline profiles will be presented by treatment.

An outlier analysis will be performed including all individual postdose measurements (not the mean data), including all repeat and unscheduled readings. The frequency of subjects with a maximum increase from baseline in QTcB and QTcF intervals will be summarised for each treatment according to the following categories: >30, >60, and ≤ 30 ms. All incidences of >30 and >60 ms will be flagged on the listing. In addition, the frequency of subjects with QTcB and QTcF postdose values will be summarised for each treatment, according to the following

categories: >450, >480, >500, and \leq 450 ms. All incidences of >450, >480, and >500 ms will be flagged on the listing.

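### A laboratory peak first found on an unscheduled sample in Part A or B is left out of every laboratory summary, although laboratory abnormality is a primary endpoint

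*SAP*

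**What the plan says.** SAP 10.1.2 sets up two kinds of extra reading. The repeat category is for vital signs and ECGs only: "Repeat readings occur when the original vital signs or ECG result requires confirmation". Such repeats replace the reading they confirm and do enter summaries. Laboratory data fall under the other category: "All results not taken at a scheduled timepoint for other data types (eg, clinical laboratory parameters) are unscheduled". For these the rule is "Because unscheduled readings are not associated with any scheduled timepoint, they are excluded from all summaries", and the sole carve-out is written as "with the exception that they may be used as baseline, as stated in" SAP 10.1.1.

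SAP 10.6.2 plans by-treatment summaries of biochemistry and haematology with changes from baseline, flags on individual listings, and a listing of all out-of-range results by parameter and treatment. It says nothing that would bring an unscheduled result into a summary.

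For ECGs, SAP 10.6.4 does the opposite: "An outlier analysis will be performed including all individual postdose measurements (not the mean data), including all repeat and unscheduled readings".

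The protocol expects off-schedule laboratory tests. Section 7.3.2 states: "Additional clinical laboratory evaluations will be performed at other times if judged to be clinically appropriate". The liver criteria in Protocol 3.7 and 4.8 depend on confirmation, for example "ALT or AST > 5 x ULN, which is confirmed by repeat". Protocol 2.2.1 makes the incidence of laboratory abnormalities a primary safety endpoint.

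**The concern.** Scheduled safety draws are few, and the extra ones are not taken at random: they are taken mainly in subjects in whom someone suspects a problem. A rule that discards exactly those results from the tables is therefore an exclusion that depends on the outcome, and the results it removes will tend to be the high ones. The by-treatment maximum and the changes from baseline can then understate abnormalities on a primary safety endpoint. A reader comparing dose levels with placebo in the tables would not see that any value had been left out.

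**Working it through.** No sample-size or error-rate figure bears on this point. The check is a reading of the rules side by side and a count from the schedules.

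**1. Can a laboratory retest enter a summary?** Not as a repeat, because that category is restricted to vital signs and ECGs (SAP 10.1.2). It is unscheduled unless it happens to fall on a scheduled visit. SAP 10.6.2 contains no override. Use as baseline does not put a postdose value into a postdose summary.

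**2. Which results can enter?** Only those at scheduled times (Protocol Appendix 6, compared with the sample counts in Appendix 3):

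| Part | Safety laboratory times in Appendix 6 | Total | Postdose | Appendix 3 total |
|---|---|---|---|---|
| A, other cohorts | Screening, Day -1, 48 h, Follow-up | 4 | 2 | 4 |
| A, food-effect cohort | Screening, 2 x (Day -1, 48 h), Follow-up | 1 + 4 + 1 = 6 | 2 + 1 = 3 | 6 |
| B | Screening, Day -1, Days 4, 6 and 11, Follow-up | 6 | 4 | 8 |

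For the food-effect cohort, the Period 2 Day -1 sample is counted as that period's baseline. In Part B the difference of 8 - 6 = 2 matches the Day 1 and Day 10 draws for glucose and lipids. The documents do not say whether liver enzymes are run on those two samples.

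**3. Two cases to keep apart.**
- *A scheduled value is high and prompts a retest.* Laboratory retests do not replace the value they check, so the high value stays in the summary. Only the confirmation is missing, unless it falls on a scheduled visit (for example a Day 4 rise confirmed on Day 6).
- *A high value is first found off-schedule.* Neither it nor any off-schedule confirmation enters a laboratory summary.

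**4. What is lost in the second case.** SAP 10.1 reports mean, standard deviation, median, minimum and maximum. As an illustration with assumed values: one of 8 active subjects in a Part B cohort has ALT 5.5 x ULN on an unscheduled Day 8 sample, confirmed on Day 9, and 2 x ULN on Day 11. All other scheduled values in the cohort are at or below 2 x ULN.

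| Quantity | Scheduled results only | All results |
|---|---|---|
| Maximum ALT (x ULN) | 2 | 5.5 |
| Subjects with a value above 5 x ULN | 0/8 = 0% | 1/8 = 12.5% |

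The maximum is understated by 5.5 - 2 = 3.5 x ULN. If the Day 11 value is varied from 2 up to 5.5 x ULN, the gap runs from 3.5 down to 0. If ALT is also measured on Day 10 and summarised, the gap is set by the higher of the Day 10 and Day 11 values. If no unscheduled sample is drawn, the gap is 0. In a Part A cohort with 6 active subjects, one such subject is 1/6 = 16.7%.

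**5. Internal consistency.** SAP 10.1.2 bars unscheduled readings from all summaries, while the QTc frequency table in SAP 10.6.4 is a by-treatment summary that includes them. Both cannot hold as written.

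**The case against.** The case for leaving the plan alone has real substance.

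- **The values are displayed.** SAP 10.6.2 lists all out-of-range results by parameter and treatment, with no carve-out for unscheduled ones. With 6 or 8 active subjects per cohort, such a listing shows every case. This stands, but a listing gives no counts or percentages by dose against placebo.
- **Other outputs may catch the subject.** Protocol Appendix 1 allows a clinically significant laboratory finding to be an adverse event, and SAP 10.6.1 tabulates treatment-emergent events. This also stands, but it depends on a judgement of clinical significance and does not produce a laboratory table.
- **Conduct is unaffected.** Escalation rests on review of all available blinded data and interim safety reports (Protocol 3.6). Agreed: the issue is reporting.
- **Leaving readings with no timepoint out of by-timepoint summaries is sensible.** Agreed, and the fix keeps that. SAP 10.6.2 also describes no table of ULN multiples even for scheduled values. The table shells, which might show more, are a separate document.

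Some stronger inferences are tempting but unsupported. A reader might infer that dropping retests hides the liver signal they confirm; it does not, because a scheduled trigger value remains. A reader might take the liver as the one organ with both a nonclinical signal and a dosing stop. QTc has both as well (Protocol 1.3, 1.4 and 4.8), which may be why it received its own table. The ALT finding, "increased serum ALT with 10 mg/kg GB1211 BID in 1 study", came from a carbon tetrachloride fibrosis model, and the 6-week mouse study found no effect on clinical pathology (Protocol 1.4). A reader might also infer that an affected subject would look near-normal in the tables, but 2 x ULN in the illustration is abnormal. Nor can one say that Part B has no laboratory draw between Days 6 and 11, given the Day 10 sample.

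**Conclusion.** The point holds in a limited form. As written, SAP 10.1.2 and 10.6.2 keep any postdose laboratory peak first found off-schedule in Parts A and B out of the maximum and change-from-baseline summaries. Confirmation status is likewise absent unless the retest falls on a scheduled visit. Such values remain in listings and may reach the adverse event tables.

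The size is contingent: zero without unscheduled samples, and one subject in 6 or 8 for each affected active subject per cohort. The direction rests on the assumption that extra samples go mainly to subjects with a suspected problem, which the wording of Protocol 7.3.2 supports. The case rests on the primary endpoint and on the protocol's confirmation-based liver criteria, not on the nonclinical ALT finding. It does not extend to Part C, which SAP 6.3 places outside this plan. The conflict between SAP 10.1.2 and 10.6.4 needs correcting whether or not any unscheduled sample is taken.

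**What to change.** - **SAP 10.1.2:** confine the exclusion of unscheduled readings to by-timepoint summaries, and name the outlier analysis in SAP 10.6.4 as an exception.
- **SAP 10.6.2:** add one table for Part A and one for Part B, by treatment including placebo, of each subject's worst postdose ALT, AST, ALP, GGT and total bilirubin over all scheduled and unscheduled results. Categorise at the multiples already in Protocol 3.7 and 4.8: 3 x and 5 x ULN for ALT and AST, 2 x and 3 x ULN for total bilirubin, and 3 x ULN for ALP and GGT. Add a count of subjects meeting the combined ALT/AST plus bilirubin condition of Protocol 4.8.
- **Footnote:** give the number of postdose samples per subject, because a subject sampled more often has more chances of a high worst value.

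The cost is a few lines of SAP text and one table shell per part. The data are already collected, no clinical rule changes, and the approach mirrors what the SAP already does for QTc.

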10.2 Demographics and Subject Disposition

The demographic variables age, sex, race, ethnicity, body weight, height, and body mass index will be summarised and listed. Subject disposition will be summarised and listed.

10.3 Pharmacokinetic Assessment

The following pharmacokinetic parameters will be determined where possible from the concentrations of GB1211 using non-compartmental methods performed using Phoenix WinNonlin (Certara, Inc., Version 8.1 or higher):

Part A (Single Dose)

Plasma

Parameter	Definition
$AUC_{0-t_{last}}$	Area under the plasma concentration-time curve from time zero to the time of the last quantifiable concentration
$AUC_{0-\infty}$	Area under the plasma concentration-time curve from time zero to infinity
$\%AUC_{extrap}$	Area under the plasma concentration-time curve extrapolated from last quantifiable concentration to infinity as a percentage of total AUC
C_{max}	Maximum observed plasma concentration
T_{max}	Time of the maximum observed plasma concentration
$t_{1/2}$	Apparent plasma terminal elimination half-life
CL/F	Apparent total plasma clearance
V_z/F	Apparent volume of distribution during the terminal elimination phase

Urine

Parameter	Definition
A_e	Amount of drug excreted unchanged in urine (and cumulative A_e)
f_e	Percentage of dose excreted unchanged in urine (and cumulative f_e)
CL _R	Renal clearance

Parts B and C (Multiple Dose)

Plasma

Parameter	Definition
$AUC_{0-\tau}$	Area under the plasma concentration-time curve over a dosing interval ($\tau = 12$ hours)
$AUC_{0-\infty}$	Area under the plasma concentration-time curve from time zero to infinity (Day 1 only)
$\%AUC_{extrap}$	Area under the plasma concentration-time curve extrapolated from last quantifiable concentration to infinity as a percentage of total AUC (Day 1 only)
C_{max}	Maximum observed plasma concentration
C_{min}	Minimum observed plasma concentration
T_{max}	Time of the maximum observed plasma concentration
$t_{1/2}$	Apparent plasma terminal elimination half-life
CL/F	Apparent total plasma clearance
V_z/F	Apparent volume of distribution during the terminal elimination phase
$RA_{AUC_{0-\tau}}$	Observed accumulation ratio based on $AUC_{0-\tau}$
$RA_{C_{max}}$	Observed accumulation ratio based on C_{max}

In addition, dose and body weight normalised values (norm) for $AUC_{0-t_{last}}$, $AUC_{0-\tau}$, $AUC_{0-\infty}$ and C_{max} will be determined by dividing the original PK parameter by mg/kg.

Additional pharmacokinetic parameters may be determined where appropriate.

Pharmacokinetic analysis will, where possible, be carried out using actual postdose times recorded in the raw data. If actual sampling times are missing, nominal times may be used.

Concentrations are used as supplied by the analytical laboratory for PK analysis. The units of concentration and resulting PK parameters, with amount or concentration in the unit, will be presented as they are received from the analytical laboratory.

C_{\max} , C_{\min} and T_{\max} will be obtained directly from the plasma concentration-time profiles.

For multiple peaks, the highest postdose concentration will be reported as C_{\max} . In the case that multiple peaks are of equal magnitude, the earliest T_{\max} will be reported.

AUC will be calculated using the linear trapezoidal method when concentrations are increasing and the logarithmic trapezoidal method when concentrations are decreasing (linear up/log down rule).

The parameters based on observed C_{last} will be reported.

The amount excreted in urine (A_e) for each urine collection interval will be calculated as the product of urine concentration and urine volume; Cumulative A_e will be calculated by summing the A_e values for each collection interval over the 0-48 h period.

The percent of the dose excreted (f_e) will be calculated for each urine collection interval (i) and cumulatively over 0-48 h according to the following formula:

$$f_e(i) = \frac{A_e(i)}{\text{dose}} \times 100$$

CL_R will be calculated according to the following formula:

$$CL_{R0-xh} = \frac{Ae_{0-xh}}{AUC_{0-xh}}$$

where 0-x h represents a common cumulative time interval (eg, 0 to 48 hours after dosing).

10.3.1 Criteria for Handling Concentrations Below the Limit of Quantification in Pharmacokinetic Analysis

- Concentration values that are below the level of quantification (BLQ) will be set to zero, with defined exceptions as follows;
 - Any embedded BLQ value (between 2 quantifiable concentrations) and BLQ values following the last quantifiable concentration in a profile will be set to missing for the purposes of PK analysis.

- If there are late positive concentration values following 2 BLQ concentration values in the apparent terminal phase, these values will be evaluated. If these values are considered to be anomalous, they will be set to missing.
- If an entire concentration-time profile is BLQ, the profile will be excluded from the PK analysis.

10.3.2 Criteria for the Calculation of an Apparent Terminal Elimination Half-Life Number of Data Points

- At least three data points will be included in the regression analysis and preferably should not include C_{max} .

10.3.2.1 Goodness of Fit

- When assessing terminal elimination phases, the R^2 adjusted value will be used as a measure of the goodness of fit of the data points to the determined line.
- An elimination half-life will only be calculated if the R^2 adjusted value of the regression line is greater than or equal to 0.7.

10.3.2.2 Period of Estimation

- Time period used for the estimation of apparent plasma terminal elimination half-lives, where possible, will be over at least two half-lives.
- Where an apparent plasma terminal elimination half-life is estimated over a time period of less than twice their resultant half-life the robustness of the value should be discussed in the study report.

10.3.2.3 Calculation of AUC

- The minimum requirement for the calculation of AUC will be the inclusion of at least three consecutive plasma concentrations above the lower limit of quantification (LLOQ), with at least one of these concentrations following C_{max} .
- For any partial AUC determination (i.e. AUC over a dosing interval), nominal time will generally be used for the end of the interval. Actual times for partial AUC intervals may be used at the discretion of the Pharmacokineticist.
- $AUC_{0-\infty}$ values where the percentage extrapolation is less than 20% will be reported. $AUC_{0-\infty}$ values where the percentage extrapolation is greater than 20% may be excluded from descriptive statistics as discretion of pharmacokineticist

10.3.2.4 Anomalous Values

- If a value is considered to be anomalous due to being inconsistent with the expected pharmacokinetic profile, it may be appropriate to exclude this point from the

pharmacokinetic analysis. However, the exclusion of data must have strong justification and will be documented in the raw data and study report.

10.4 Presentation of Pharmacokinetic Data

10.4.1 Presentation Pharmacokinetic Concentration Data

- The following rules will be applied if there are values that are BLQ or if there are missing values (e.g., no result [NR]) in a concentration data series to be summarised.
 - For the calculation of summary statistics, BLQ values will be set to zero.
 - If an embedded BLQ value is considered anomalous within the concentration-time profile, this value will be excluded from the summary statistics.
 - Where there is NR, these will be set to missing.
 - If there are less than three values in the data series, only the min, max and N will be presented. The other summary statistics will be denoted as not calculated (NC). BLQ is considered a value.
 - If all the values are BLQ, then the arithmetic mean, arithmetic SD, median, min and max will be presented as zero, and the geometric mean and geometric CV% will be denoted as NC.
 - If the value of the arithmetic mean or median is below the lower limit of quantification, these values will be presented as zero and the geometric mean and geometric CV% will be denoted as NC.

